4.3.4. Immunogenicity Endpoints

The following immunology endpoints will be analyzed:

- ELISpot results will be presented by scheduled visit and increase from baseline will be analyzed using an exact non-parametric 95% CI on the median at each time point after baseline (Weeks 15, 36, and 88).
- HPV-16 and HPV-18 E7-specific ELISA results will be presented by scheduled visit and analyzed using geometric mean titers and t-distribution 95% CI on the geometric mean titer at each time point after baseline (Weeks 15, 36, and 88).
- Increase from baseline in frequency of VGX-3100-specific CD8+/CD137+ peripheral blood mononuclear cells that are Perforin+ will be analyzed using an exact non-parametric 95% CI on the median.

- Change from baseline in proinflammatory and immunosuppressive elements in tissue based on nanostring assays will be analyzed using a t-distribution based 95% CI on the mean.

All immunogenicity data will be presented by study visit in data listings.

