1.1.5.3. Exploratory Objectives

The exploratory objectives include the following:

- To describe the long-term efficacy of VGX-3100 with respect to combined histopathologic regression of anal or anal/peri-anal HSIL and virologic clearance of HPV-16 and/or HPV-18
- To describe the long-term efficacy of VGX-3100, as measured by histologic regression of anal or anal/peri-anal HSIL
- To describe the long-term efficacy of VGX-3100, as measured by virologic clearance of HPV-16 and/or HPV-18 by testing from lesion tissue
- To describe the long-term efficacy of VGX-3100, as measured by virologic clearance of HPV-16 and/or HPV-18 by intra-anal swab testing
- To evaluate tissue immune responses to VGX-3100 in intra-anal and/or peri-anal samples
- To describe the clearance of HPV-16 and/or HPV-18 infection from non-anal anatomic locations
- To describe the association of microRNA (miRNA) profile, previous anoscopy, cytology, and HPV testing results with Week 36 histologic regression
- To describe the patient reported outcomes (PRO) for subjects treated with VGX-3100
- To determine the humoral and cellular immune response following administration of VGX-3100 at post dose 3, and after additional dosing compared to baseline
- To determine the long-term efficacy of VGX-3100 with respect to histopathologic regression of anal or anal/peri-anal HSIL or virologic clearance of HPV-16 and/or HPV-18

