1.2.5.2. Immunology Parameters

A secondary immunology endpoint is the flow cytometry response magnitude from the Lytic Granule Loading assay at baseline and Week 15 visits. The Lytic Granule Loading assay may examine the following external cellular markers: CD3, CD4, CD8 (T cell identification), CD137, CD38, and CD69 (T cell activation markers) as well as PD-1 (exhaustion/activation marker).

Exploratory immunology endpoints include the following:

- Levels of serum anti-HPV-16 and anti-HPV-18 antibody concentrations at baseline and Weeks 15, 36, and 88 visits
- Interferon- γ ELISpot response (spot forming units [SFU]) at baseline and Weeks 15, 36, and 88 visits.
- Proinflammatory and immunosuppressive elements results including, but not limited to, CD8+ and FoxP3+ infiltrating cells as well as Granulysin, Perforin, CD137, CD103 and PD-L1 in intra-anal and/or peri-anal tissue as sample allows.

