3.4. Baseline Definitions

For all analyses, baseline will be defined as the most recent measurement before the first administration of study drug.

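### The ELISA antibody analysis plans no estimate or interval for change from baseline, although the exploratory objective is a comparison with baseline (minor)

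*SAP*

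**What the plan says.** **Objective.** SAP Section 1.1.5.3 lists, as exploratory: "To determine the humoral and cellular immune response following administration of VGX-3100 at post dose 3, and after additional dosing compared to baseline".

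**Endpoint.** Section 1.2.5.2, also exploratory: "Levels of serum anti-HPV-16 and anti-HPV-18 antibody concentrations at baseline and Weeks 15, 36, and 88 visits".

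**Analysis.** The ELISA bullet in Section 4.3.4 has two parts. The first is a display: "HPV-16 and HPV-18 E7-specific ELISA results will be presented by scheduled visit". The second is the estimate and its interval: "geometric mean titers and t-distribution 95% CI on the geometric mean titer at each time point after baseline", with Weeks 15, 36 and 88 named.

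**Neighbouring bullets in Section 4.3.4.** For ELISpot, "increase from baseline will be analyzed using an exact non-parametric 95% CI on the median". For flow cytometry, the quantity is "Increase from baseline in frequency of VGX-3100-specific CD8+/CD137+ peripheral blood mononuclear cells" (those that are Perforin-positive). For the tissue markers, it is "Change from baseline in proinflammatory and immunosuppressive elements in tissue".

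**Baseline.** Section 3.4: "baseline will be defined as the most recent measurement before the first administration of study drug". Note 6 to Table 1 asks for at least 8 mL of serum before the first dose.

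**The concern.** The objective asks for a contrast between later visits and baseline. The statistic fixed for ELISA is a level at each later visit. The two differ, and ELISA is the only one of the four immune measures in the list whose specified estimate is not referenced to baseline. The SAP gives no reason for this.

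The difference matters because of the design. The study is open-label with one treatment (Sections 1.2.1 and 1.2.2), so no concurrent control shows what titres would have been without dosing. Every subject enters with lesion tissue positive for HPV-16 and/or HPV-18, so some anti-E7 antibody before dosing cannot be excluded. Each subject's own baseline is then the only reference within the trial. What is at stake is how well the study report can answer one exploratory question. No confirmatory conclusion depends on it.

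**Working it through.** **1. Is there a plan figure to reproduce?** Not on this point: the SAP gives no titre, titre SD or correlation. Its one design figure, about 80% power in Section 3.1, uses 24 subjects, 90% evaluable, 40% versus 15% and one-sided 0.05. It reproduces: 24 × 0.9 = 21.6; with n = 21, the exact binomial rule rejects at 7 or more responders, with power 0.80. No antibody quantity enters it.

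**2. The texts side by side (Section 4.3.4).**

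| Measure | Estimate specified | Referenced to baseline? |
|---|---|---|
| ELISpot | median increase, exact CI | yes |
| CD8+/CD137+ Perforin+ cells | median increase, exact CI | yes |
| Tissue markers | mean change, t-based CI | yes |
| E7 ELISA | GMT at Weeks 15, 36, 88, t-based CI | no |

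No other section supplies a fold rise, paired contrast or seroresponse for ELISA. Section 3.2 adds only descriptive tabulations, and the end of Section 4.3.4 adds listings by visit.

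**3. What the planned statistic estimates.** Let Tᵢᵥ be the titre of subject i at visit v, with v = 0 for baseline.

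- Planned: GMTᵥ = 10^mean(log₁₀Tᵢᵥ), with CI factor 10^(t·sᵥ/√n), where sᵥ is the SD of log₁₀ titre at that visit.
- What the objective asks for: dᵢ = log₁₀Tᵢᵥ − log₁₀Tᵢ₀; fold rise = 10^mean(dᵢ), with CI factor 10^(t·s_d/√n), where s_d² = s₀² + sᵥ² − 2ρs₀sᵥ and ρ is the baseline-to-visit correlation.

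For subjects measured at both visits, mean(dᵢ) is the difference of the two log means, so fold rise = GMTᵥ/GMT₀. The point estimate could therefore be recovered if the baseline GMT were shown for the same subjects. The interval could not, because it needs s_d.

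**4. The post-dose GMT alone does not fix the fold rise.** Assume a post-dose GMT of 200:

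- baseline 25: 200/25 = 8
- baseline 50: 200/50 = 4
- baseline 100: 200/100 = 2
- baseline 200: 200/200 = 1 (no rise)

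The planned estimate and interval are identical in all four cases.

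**5. The GMT interval does not fix the fold-rise interval.** Assume n = 22 (21.6 rounded up), t = 2.080 on 21 degrees of freedom, and a log₁₀ SD of 0.6 at both visits. The GMT factor is 10^(2.080 × 0.6/√22) = 10^0.266 = 1.85. For the fold rise, s_d = 0.6·√(2(1 − ρ)):

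| ρ (assumed) | 0 | 0.3 | 0.5 | 0.7 | 0.9 |
|---|---|---|---|---|---|
| Fold-rise CI factor | 2.38 | 2.06 | 1.85 | 1.61 | 1.32 |

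Over SDs of 0.4 to 0.8 and ρ of 0 to 0.9, the factor runs from 1.20 to 3.17. These figures show only that one interval cannot stand in for the other; they do not measure an error in the SAP.

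**6. Sensitivity of the fold rise to undetectable titres.** Suppose the value substituted below the assay limit is multiplied by k at all visits. A subject undetectable at both visits keeps a ratio of 1. If a proportion p goes from undetectable to detectable and a proportion q the other way, the fold rise is multiplied by k^(q − p). With p near 0 and q near 0 this is negligible. With p near 1, the fold rise scales almost inversely with the chosen value.

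**The case against.** The strongest reply has four parts.

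- **Display by visit.** ELISA results are tabulated by visit and listed by subject, and baseline is a defined sampling time for this endpoint. A reader might infer from the estimate alone that antibody is reported only after baseline and that a rise cannot be seen at all. The SAP does not support that: baseline titres may well be displayed, and a rise could be read from them descriptively. What remains is that no estimate of the change and no interval for it is planned. ELISpot gets the same display by visit, and the SAP still adds an interval on the increase there.
- **The endpoint is a level.** Section 1.2.5.2 defines antibody levels, and a GMT summarises levels. This is correct, so the mismatch is with the objective's baseline comparison and not with the endpoint's wording.
- **Pre-existing antibody is not shown.** A reader might take HPV-16/18-positive lesions to mean that subjects already carry anti-E7 antibody. The SAP gives no baseline serology, and positive tissue does not establish it. If baseline titres are mostly undetectable, the post-dose GMT comes close to showing the response. The point needs only that the plan cannot tell these cases apart without the baseline.
- **Low stakes.** Humoral response is exploratory, the secondary immune objective in Section 1.1.5.2 is cellular, and Section 3.2 confines formal testing to the primary endpoint. A fold rise could be computed later from the stored data. All this stands and limits the severity.

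It is also tempting to quote a precision gain from pairing over an unpaired comparison of two visit GMTs. The SAP plans no such unpaired comparison and gives no correlation, so no such gain is claimed. The table shells are a separate document and could carry a change row; that cannot be checked here.

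**Conclusion.** The point holds as a minor one. Section 4.3.4 plans an ELISA estimate and interval only for the GMT at each post-baseline visit, whereas the exploratory objective is a comparison with baseline and the three companion measures are analysed that way. Baseline titres may be displayed, but the within-subject change and its interval are not planned.

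The SAP gives no figure from which to size the effect on results. The titres, SDs and correlations used above are assumptions that show only what the planned statistic leaves undetermined. The primary test, power and sample size are unaffected.

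**What to change.** Extend the ELISA bullet in Section 4.3.4 as follows:

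- Add, for HPV-16 and HPV-18 separately, the geometric mean fold rise from baseline at Weeks 15, 36 and 88, with a t-based 95% CI computed on the within-subject log ratio and back-transformed, in subjects with a titre at both visits.
- Keep the planned GMTs and report the baseline GMT beside them.
- State one substitution for titres below the assay limit, applied at every visit and fixed before results are seen.

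**Cost.** One more statistic per antigen and visit, from sera already planned; no new visit, sample or assay. The small downside is that the fold rise depends on the substituted value when many baseline titres are undetectable. Reporting the number below the limit at each visit would let the reader judge this.

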4.4. Safety Analyses

Safety analyses will be conducted using the Safety population.

4.4.1. Study Drug Exposure

Study drug exposure will be tabulated by the number of doses received. The number and percentage of subjects will be reported.

Compliance will be measured by the following parameters: success of EP, the location of the EP treatment, the size of EP array, and whether or not a guide was used.

Dosing information for each subject will be presented in a data listing.

4.4.2. Adverse Events

All AEs will be coded using the most current version of the MedDRA coding system and displayed in tables and data listings using system organ class (SOC) and preferred term.

Analyses of AEs will be performed for those events that are considered treatment-emergent, where treatment-emergent is defined per protocol as any AE with onset after the administration of study medication through the end of the study (i.e., study discharge).

An AESI is defined as an AE deemed related to VGX-3100 delivered with CELLECTRA™ 5PSP that requires expedited communication from the site to the Sponsor and meets any of the following criteria per the Toxicity Grade for Healthy Adults:

- Grade 3 or greater persistent administration site erythema, and/or induration recorded ≥ 2 hours immediately after study treatment
- Grade 4 or greater persistent administration site pain, tenderness recorded ≥ 2 hours immediately after study treatment
- Grade 3 or greater fewer
- Grade 3 or greater systemic symptoms, including generalized pruritus

Separate summaries of AEs will be presented for events with an onset within the first 7 and 28 days after injection and overall. The summary will include the number and percentage of subjects with any treatment-emergent AE (TEAE), any TEAE assessed by the Investigator as related to treatment, any AESI, any TEAE by Common Terminology Criteria for Adverse Events (CTCAE v4.03) grade, any SAE, any pre-treatment AE, any AE leading to discontinuation of treatment, and any AE leading to death.

In these tabulations, each subject will contribute only once (i.e., the most related occurrence or the most intense occurrence) to each of the incidences in the analysis, regardless of the number of episodes. In addition to the number of subjects that experienced at least 1 of the events, the total number of events observed across subjects will also be reported.

Summary tables by SOC and preferred term will be produced for the following:

- All TEAEs
- All TEAEs by most recent injection
- All TEAEs by severity grade
- All TEAE assessed as at least possibly related to treatment by the Investigator (i.e., treatment-related)
- All TEAEs with onset within 7 days of an injection
- All TEAEs with onset within 7 days by severity grade
- All treatment-related TEAEs with onset within 7 days of an injection
- All TEAEs with onset within 28 days of an injection
- All TEAEs with onset within 28 days of an injection by severity grade
- All treatment-related TEAEs with onset within 28 days of an injection

For each tabulation, TEAEs are summarized by proportions of subjects; therefore, in any tabulation, a subject contributes only once to the count for a given TEAE (SOC or preferred term), irrespective of the number of episodes of a particular AE term reported. Injection site reactions are included in the TEAE summaries. The frequency of subjects with preferred term events with onset within 7 days and, separately, within 28 days after dosing will be summarized with percentages and exact Clopper-Pearson 95% CIs.

All AEs occurring on-study will be listed in subject data listings. By-subject listings also will be provided for the following: AEs leading to death, SAEs, AEs with severity \geq Grade 3, AEs leading to discontinuation of treatment, and AESIs.

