1.2. Study Design

1.2.1. Synopsis of Study Design

HPV-203 is a Phase 2, open-label efficacy study of VGX-3100 (DNA plasmids encoding E6 and E7 proteins of HPV types 16 and 18) administered by IM injection followed by EP in adult men and women who are HIV negative with histologically confirmed anal or anal/peri-anal

HSIL associated with HPV-16 and/or HPV-18. Approximately 24 subjects will receive at least 3 doses of VGX-3100. Each dose of VGX-3100 will be administered IM in a 1-mL volume followed immediately by EP.

To be eligible for the study, subjects must consent to participate and agree to the collection of anal lesion tissue samples for anal cytology and genotyping, a Digital Anal Rectal Examination (DARE), blood samples for immunologic assessments, high-resolution anoscopy (HRA) and HRA-guided biopsies. All intra-anal and/or peri-anal lesion(s) of adequate size ($\geq 4\text{mm}$) will be biopsied at Screening. Biopsy slides will be sent to a Pathology Adjudication Committee (PAC) for evaluation before enrollment. To be eligible for enrollment, the PAC must assign the diagnosis of anal or anal/peri-anal HSIL (AIN2, AIN3, PAIN2, PAIN3) based on the biopsy sample(s). Subjects must also have intra-anal and/or peri-anal lesion tissue test positive for HPV genotype 16 and/or 18 to be eligible for participation in the study.

Depending upon their disposition with regard to histologic and lesion area changes during the trial, all eligible subjects who consent to participate in the HPV-203 study will receive at least three doses of VGX-3100 (6 mg in 1 mL) administered IM (deltoid, preferred site, or anterolateral quadriceps, alternate site), each followed immediately by EP with the CELLECTRA™ 5PSP device. The first study treatment will be administered on Day 0, the second at Week 4, and the third at Week 12. Partial response to VGX-3100 may still be of medical importance by being able to limit the extent of surgery necessary. For partial responders at Week 36, a fourth dose may be administered at Week 40.

To assess quality of life and related impacts on subjects, PRO instruments will be provided and will include the Short Form Health Survey version 2 (SF-36v2™), the EQ-5D-5L, and 2 additional PRO questions assessing quality of life after surgery or biopsy.

The total duration of the study is up to 10 weeks for the screening period and up to 88 weeks for the treatment and follow-up periods.

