3.10. Missing, Unused, and Spurious Data

When tabulating AE data, partial dates will be handled as follows in order to determine treatment emergence. If any of the day, month, or year is missing, the onset date will be set to the earliest date that is consistent with any non-missing date information, unless the non-missing date information is the same as study treatment start. In this case, in order to conservatively report the event as treatment-emergent, the onset date will be assumed to be the date of start of treatment. A completely missing onset date will be coded as the day of start of treatment.

A prior medication is defined as any medication that was used and has a stop date before the start of the trial (before Dose #1 on Day 0). A concomitant medication is defined as any medication that has a stop date that is on or after the date of first dose of study drug. For prior and concomitant medications, partial start dates will not be imputed, as stop dates determine prior versus concomitant. Partial stop dates will be assumed to be the latest possible date consistent with the partial date.

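### Treatment emergence rests on onset date alone, so a screening-period AE that worsens after a dose is left out of every TEAE table unless the worsening is logged as a new AE

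*SAP*

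**What the plan says.** Section 4.4.2 sets the scope first: "Analyses of AEs will be performed for those events that are considered treatment-emergent". It then gives the criterion: "treatment-emergent is defined per protocol as any AE with onset after the administration of study medication through the end of the study". Neither sentence mentions an event that was already present and then got worse.

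Section 3.10 supplies the date rule. There, "partial dates will be handled as follows in order to determine treatment emergence", and what follows concerns the onset date only. It contains nothing about a change of grade.

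The SAP does expect AEs before dosing to be recorded. The overall AE summary in Section 4.4.2 includes "any pre-treatment AE" as its own entry. Section 1.2.1 allows a long run-in ("The total duration of the study is up to 10 weeks for the screening period") and says that intra-anal and peri-anal lesions of at least 4 mm "will be biopsied at Screening".

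Outside the tables, Section 4.4.2 also provides that "All AEs occurring on-study will be listed in subject data listings". It plans separate listings for AEs of Grade 3 or higher, SAEs, AESIs, and AEs leading to discontinuation or death.

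**The concern.** A TEAE definition usually has two limbs: new events after dosing, and existing events that worsen after dosing. This one has only the first. If an ongoing screening-period AE becomes more severe after a dose, the tables treat it like an AE that never changed. That holds even if the investigator attributes the worsening to treatment, because the treatment-related tables are also restricted to TEAEs.

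The omission works in one direction. Adding worsened events can only raise, or leave unchanged, the number of subjects with a given term, with a related event, or with an event at or above a given grade. Evaluating safety and tolerability is a secondary objective, and the trial has a single arm, so no control group shares the omission. The rule also runs against the SAP's own approach in Section 3.10, where doubtful onset dates are resolved towards treatment emergence so as to be conservative.

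**Working it through.** The SAP gives no figure that depends on this definition, so there is none to reproduce. The check is to follow one record through the planned outputs and then give the scale.

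**Step 1. One record.** Take an AE that starts in screening, is still present at Day 0, and goes from Grade 1 to Grade 3 within 7 days of a dose. It is recorded as a single AE with its true onset date.

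- Section 4.4.2 criterion: onset must follow administration. It does not, so the event is not a TEAE.
- Section 3.10: the onset date is complete, so no imputation applies and the result is unchanged.
- The rest of the SAP: no rule on worsening, and no statement that worsening opens a new record.

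**Step 2. Where the record appears.**

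| Output in Section 4.4.2 | Included? |
|---|---|
| SOC/preferred-term tables: all TEAEs, by most recent injection, by severity, treatment-related (4 tables) | No |
| SOC/preferred-term tables within 7 days: all, by severity, treatment-related (3 tables) | No |
| SOC/preferred-term tables within 28 days: all, by severity, treatment-related (3 tables) | No |
| 7-day and 28-day preferred-term frequencies with exact intervals | No (tied to onset) |
| Overall summary rows labelled TEAE (any, related, by grade) | No |
| Overall summary row for pre-treatment AEs | Yes |
| Overall summary rows for AESI, SAE, discontinuation and death | Unclear: not labelled TEAE, but under the general restriction to TEAEs |
| By-subject listings, including Grade 3 or higher | Yes (the Grade 3 listing if the worst grade is recorded) |

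The tables number 4 + 3 + 3 = 10, and the event is absent from all ten. The wording "any pre-treatment AE, any AE leading to discontinuation of treatment, and any AE leading to death" shows that the overall summary is not strictly confined to TEAEs, which is why the four rows above cannot be settled from the text.

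**Step 3. Scale.** Input: 24 subjects (Section 3.1), assumed all treated. One subject is 1/24 = 4.2 percentage points.

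Illustration for a preferred term with no other case, using the Clopper-Pearson method the SAP specifies for the windowed frequencies:

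- Worsening excluded: 0/24 = 0%. The upper limit is 1 − 0.025^(1/24) = 0.142, so the 95% CI is 0 to 14.2%.
- Worsening included: 1/24 = 4.2%. The lower limit is 1 − 0.975^(1/24) = 0.001. The upper limit is the 0.975 quantile of Beta(2, 23) = 0.211. The 95% CI is 0.1% to 21.1%.

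The 4.2 points apply only if the subject is not already counted in the same row. A subject with another TEAE of that term leaves the term's incidence unchanged. A subject with another event of that term at the same or a higher grade leaves the by-severity count unchanged.

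**The case against.** The strongest reply is that the SAP takes this definition from the protocol, and that how sites record a worsening is normally settled in the protocol or CRF instructions. If a grade increase is always entered as a new AE, the event has a post-dose onset and reaches the tables, and the effect is zero. This limits the size of the point but does not remove it. The SAP adopts the definition as its analysis rule and states no such convention, so as written the rule excludes these events.

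Second, a reader might infer that such an event is counted solely as a pre-treatment AE and otherwise disappears. The SAP does not support that. The listings carry it, and with about 24 subjects they can be read in full. What stands is that listings do not correct tabulated rates.

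Third, a reader might infer from the 10-week screening period and the screening biopsies that AEs ongoing at Day 0 are to be expected. The SAP gives no count of pre-dose AEs and does not say that biopsy effects persist to dosing. A long interval also gives them time to resolve. The design makes such events possible and shows no more than that.

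Fourth, several main tolerability signals are largely untouched. A reaction at the first injection site cannot precede that injection. Local and systemic events in the 7 days after each dose are a separate diary-card endpoint (Section 1.2.5.3). Safety laboratory data are collected at Screening (Section 4.4.3), so worsening laboratory values are an unlikely route. No safety hypothesis is tested (Section 3.2). All of this is fair, and it keeps the point minor.

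**Conclusion.** The point holds in a limited form. On the SAP's wording, an AE that starts in screening and increases in grade or becomes serious after a dose is absent from every TEAE table by system organ class and preferred term. This assumes that the worsening is not recorded as a new AE, which the SAP leaves unstated. The protocol was not examined, so its recording rule is unknown here.

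The number of subjects affected is unknown and may be zero. Each one not otherwise counted in a row lowers that row by 4.2 percentage points, on the assumption of 24 treated subjects. A reader might go further and put a figure on the understatement of Grade 3 rates, for example 2/24 = 8.3 points for two subjects. The SAP gives no basis for the number two, and the figure would also require that neither subject had any other Grade 3 TEAE. No efficacy result or formal test is affected.

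**What to change.** In Section 4.4.2, define a TEAE as an AE with onset after the first administration, or an AE present before it that increases in severity grade or becomes serious after it. For the second kind, use the date of worsening in the 7-day, 28-day and by-injection tables, and extend the partial-date rule in Section 3.10 to that date.

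Alternatively, if sites already record worsening as a new AE with its own onset date, say so in Section 4.4.2. The present definition then suffices.

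Section 5 currently declares no changes from the protocol. If the revised definition differs from the protocol's, list it there. It would also help to state whether the summary rows for AESI, SAE, discontinuation and death are limited to TEAEs.

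The cost is a sentence or two, one programming rule, and a grade-change date or new AE record for events ongoing at dosing. Reported TEAE rates may be slightly higher.

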1.2.4. Study Procedures

The schedule of assessments, as outlined in the study protocol, is provided in [Table 1](#)

Table 1: Schedule of Assessments

Study Action				Screening (-10 wk. to -1d)	Day 0								
Informed consent	X												
Medical History/Demographics	X												
Medications (prior/concomitant)	X	X		X		X	X	X	X	X	X	X	
Socio-behavioral assessment	X									X		X ¹⁵	X
Inclusion/Exclusion criteria ¹	X	X											
Physical exam (PE)/assessment ²	X	X		X		X	X	X	X	X	X	X	X
Vital signs	X ³	X		X		X	X	X	X	X	X	X	X
Screening safety (12 lead ECG, laboratories) ⁴	X												
Pregnancy Testing ⁵	X	X		X		X	X	X	X	X	X	X	X
HIV Ab by ELISA	X									X			
Blood immunologic samples	X ⁶	X ⁶					X ⁷		X ⁶				X ⁶
Oropharyngeal (OP) rinse		X		X			X	X	X			X	X
Vaginal, cervical, and penile swab		X		X			X	X	X			X	X
Intra-anal and/or peri-anal swab	X	X		X			X	X	X			X	X
Digital Anal Rectal Examination DARE ⁸	X	X		X			X	X	X			X	X
High Resolution Anoscopy (HRA) ⁹	X	X		X			X	X	X			X	X
Lesion photography ¹⁰	X	X		X			X	X	X			X	X
Biopsy ¹¹	X								X			X ¹⁸	

Study Action	Timeline											
	Screening (-10 wk. to -1d)	Day 0	8-14 days post dose 1 Phone Call	Week 4 (\pm 4 days)	8-14 days post dose 2 Phone Call	Week 12 (\pm 4 days)	Week 15 (\pm 1 Week)	Week 28 (\pm 1 Week)	Week 36 (\pm 1 Week)	Week 40 (\pm 1 Week)	8-14 days post dose 4 Phone Call	Week 64 (\pm 2 Weeks)
Inject VGX-3100 +EP ¹²	X		X	X		X				X ¹²		
Post treatment reaction assessment	X		X	X		X				X		
Distribute Participant Diary Card (PDC)	X		X	X		X				X		
Review PDC ¹³			X	X	X	X	X			X	X	
Patient Reported Outcomes (PROs) (SF-36v2 TM) (EQ-5D-5L) ¹⁴		X ¹⁶	X	X	X	X	X	X	X	X ¹⁷	X	X

1. Subject eligibility will be reconfirmed at every visit.
2. Full physical exam (PE) mandatory at Screening and study discharge (Week 88), otherwise targeted PE as determined by the Investigator or per subject complaints unless signs or symptoms dictate the need for a full PE.
3. Screening vital signs must include a measured height and weight and calculated body mass index (BMI) (Bodyweight in kilograms divided by height in meters squared). Weight will be collected at all dosing visits.
4. Screening 12-lead electrocardiogram (ECG), complete blood count (CBC), serum electrolytes, blood urea nitrogen (BUN), creatinine (Cr), glucose, alanine aminotransferase (ALT), and creatine phosphokinase (CPK) performed within 45 days before first dose administration.

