1.2.5.3. Safety Parameters

Safety evaluations performed during the study included physical examinations, measurement of vital signs, 12-lead ECGs, clinical laboratory evaluations including hematology, serum chemistry, and CPK, and monitoring of AEs, including injection site reactions.

The secondary safety endpoints are:

- Local and systemic events for 7 days after each dose as noted in the Participant Diary Card
- All AEs including SAEs, unanticipated (serious) adverse device effect, and other unexpected AEs for the duration of the study (through the Week 88 visit)

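### Tolerability in the 7 days after each dose cannot be read from the planned summary tables: the fixed-window tables pool all injections, and the one by-dose table covers unequal follow-up.

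*SAP*

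**What the plan says.** SAP section 1.2.5.3 lists as a secondary safety endpoint "Local and systemic events for 7 days after each dose as noted in the Participant Diary Card".

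Section 4.4.2 then lists the tables by system organ class and preferred term. The fixed-window ones are "All TEAEs with onset within 7 days of an injection" and "All TEAEs with onset within 28 days of an injection", each with versions by severity and for treatment-related events. The interval estimates are worded the same way: "The frequency of subjects with preferred term events with onset within 7 days and, separately, within 28 days after dosing will be summarized", with exact Clopper-Pearson limits. None of these is split by dose number, and a subject counts once per term in any table.

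One table is organised by dose: "All TEAEs by most recent injection". It carries no 7- or 28-day limit. Treatment-emergent events run from dosing to study discharge, which footnote 2 to Table 1 places at Week 88.

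On dosing, section 1.2.1 states: "The first study treatment will be administered on Day 0, the second at Week 4, and the third at Week 12". The same section allows partial responders a fourth dose at Week 40.

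No section names a separate summary of the diary-card events. Section 4.4.2 includes injection site reactions in the TEAE summaries.

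**The concern.** The endpoint is tied to a short window after each dose. The planned tables give either the window without the dose or the dose without the window.

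This matters for a product given three or four times, because a natural safety question is whether reactions become more or less frequent with repeated dosing. The pooled tables cannot show that, since a reaction after one injection and the same reaction after every injection count alike. The by-dose table could mislead on it: unrelated background events accumulate for longer after later doses, so total TEAE frequencies may differ between doses for reasons unconnected with the dose itself.

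**Working it through.** **Inputs.** Doses at Day 0 and Weeks 4 and 12, with an optional fourth at Week 40 (section 1.2.1). End of the TEAE period at Week 88 (section 4.4.2; Table 1, footnote 2). Endpoint window of 7 days (section 1.2.5.3). The SAP gives no figure of its own on this point to reproduce.

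**Step 1: follow-up behind each column of the by-dose table.** Length = week of the next dose, or Week 88, minus the week of this dose. The last column is 7 days divided by that length.

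| Most recent dose | Length | Days | 7-day window as share |
|---|---|---|---|
| 1 | 4 − 0 = 4 weeks | 28 | 25% |
| 2 | 12 − 4 = 8 weeks | 56 | 12.5% |
| 3, dose 4 given | 40 − 12 = 28 weeks | 196 | 3.6% |
| 3, no dose 4 | 88 − 12 = 76 weeks | 532 | 1.3% |
| 4 | 88 − 40 = 48 weeks | 336 | 2.1% |

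The longest length is 76/4 = 19 times the shortest. Lengths are approximate because visits have windows. For example, Week 4 ± 4 days puts dose 2 between day 24 and day 32. The dose 1 column is therefore close to a 28-day window. No column is close to 7 days.

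**Step 2: what unequal follow-up does to total TEAE frequencies (illustration only).** Assume a constant background rate r per subject-week, unrelated to dose. The expected share of subjects with at least one event in w weeks is 1 − exp(−r·w). The SAP gives no rate, so r = 0.02 is shown with half and double that value.

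| r | 4 wk | 8 wk | 28 wk | 76 wk | 48 wk | 76 wk ÷ 4 wk |
|---|---|---|---|---|---|---|
| 0.01 | 3.9% | 7.7% | 24.4% | 53.2% | 38.1% | 13.6 |
| 0.02 | 7.7% | 14.8% | 42.9% | 78.1% | 61.7% | 10.2 |
| 0.04 | 14.8% | 27.4% | 67.4% | 95.2% | 85.3% | 6.4 |

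The size depends on the assumed rate. The direction does not: any constant positive rate gives larger shares over longer intervals.

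**Step 3: what pooling hides (illustration only).** Suppose a reaction occurs independently in 40% of subjects after each of three doses. The pooled once-per-subject figure is 1 − (1 − 0.4)³ = 1 − 0.216 = 78.4%. A reaction in 78.4% after dose 1 and in nobody after doses 2 and 3 gives the same 78.4%. The pooled table cannot tell the two apart.

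**The case against.** The strongest reply is that the endpoint sets an observation window and does not demand a comparison between doses. The matching objective is general safety and tolerability, and the split into 3 versus 4 doses in section 3.8 concerns efficacy only. The pooled 7-day tables, by severity and relationship and with exact intervals, do summarise that window. This stands. A reader might infer that the SAP fails to analyse its own secondary endpoint, and the document does not support that.

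Second, the information is not lost. AEs are listed by subject, dated listings carry the relative day, and dosing is listed, so with about 24 subjects a manual reconstruction is practical. This also stands, and limits the point to the summary tables.

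Third, injection-site terms would not be expected to accumulate over 76 weeks, so the by-dose table may still be informative for them. This is fair: the roughly tenfold gradient at r = 0.02 describes all TEAEs under an assumed rate and does not show that injection-site rows mislead.

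Fourth, a reader might infer that dose 4 reactions will be diluted by dividing by all treated subjects. For example, 3 reactors among 6 recipients would be 50% of those dosed but 3/24 = 12.5% of all treated. Those counts are invented. Section 4.4 names the Safety population but fixes no column denominator, and exposure is tabulated by number of doses. The dilution is a possibility that the text leaves open.

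Finally, the table shells are a separate document (section 7.2) and may add dose columns, and the overall summary also reports total events. Neither puts a by-dose, fixed-window table into the SAP text.

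**Conclusion.** The point holds for the planned summary tables. As section 4.4.2 is written, no table shows events within 7 days by dose number. The only by-dose table compares total TEAEs over follow-up of about 4, 8, 28 or 76, and 48 weeks, so its columns are not comparable. Dose 1 at about 28 days is roughly readable; no dose is readable at 7 days without going to the listings.

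The interval lengths rest only on the SAP's schedule, taken at nominal weeks. The background-rate, pooling and dose 4 figures are illustrations under assumed values and carry no weight in the conclusion. No decision rule depends on these tables, so this is a worthwhile, inexpensive improvement to a descriptive safety section.

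**What to change.** In section 4.4.2:

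- Add tables of diary-card local and systemic events, and of TEAEs, with onset within 7 days and separately within 28 days, by dose number (1 to 4).
- State the denominator as the subjects who received that dose, and count each subject once per term per dose.
- Since dose 2 may fall on day 24, state that an event is attributed to the latest preceding dose.
- Keep the pooled 7- and 28-day tables as the overall summary.
- Keep the table by most recent injection, with a footnote that follow-up differs between doses and that its frequencies should not be compared across them.

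The cost is a few sentences of SAP text and a few extra table shells, using data already collected. The drawback is that the number receiving dose 4 is unknown and may be small, so its intervals will probably be wide.
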